10.4.5 Timing of Doses for Each Participant

Upon obtaining informed consent from participants, all participants will receive a dose of influenza vaccine at day 0 (zero) by one of the three dosages and routes of administration (see section 10.1.1). After followup return visits in person to assess adverse reactions scheduled on days 2 and 7, each participant will return for a second dose of vaccine on day 28 (4 weeks), which will be followed again with return visits for adverse reactions on days 30 and 35. A final visit on day 56 (8 weeks) will be scheduled for the third and final blood draw and an "insurance" dose of full-strength vaccine administered by conventional needle-syringe. The days listed above for followup visits and actions have various margins of acceptable deviation, as listed in **Table 6** in section 10.6.1.

10.4.6 Blinding

The study will be observer-blinded. The study investigators, plus the study clinical staff who will assess and record adverse reactions, the laboratory personnel who will process and perform serological assays on the specimens, as well as the participant's parent(s) will all be unaware of the study group into which the participant is assigned. Only the

HIRRC/CDC Needle-free Intradermal	Page 73	File: 4785-ID-INF-Prot-Engl-2008Jun24.doc
Influenza Study - CDC-ISO-4785	of 138	2008-Jun-24

unblinded *injection nurse* and *holding assistant* will observe the method of injection. None of these unblinded staff will be involved in assessing or recording adverse events in the Case Report or other forms. Parents will be required to remain outside the injection room during the 1 to 2 minutes necessary to carry out the vaccination. The *allocation group randomization cards* (see 10.4.4.3) will be destroyed and discarded at the time when the device is filled for the associated participant. No written record of vaccination dose or route will be maintained in the study clinic.

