9.6.4 Research Questions

- Will the investigational study arm of children receiving two doses of 0.1 mL of influenza vaccine administered ID demonstrate *non-inferiority* to the immune responses achieved by the control study arm of children receiving two conventional, full-doses of 0.25 mL administered IM by needle-syringe? (Primary endpoint: proportion of participants achieving inverse titer of ≥40 on hemagglutination inhibition assay for each virus strain in the vaccine.)
- 2. What will be the safety profile of jet-injected, reduced-dose, intradermal influenza vaccination (erythema, induration, limb swelling, bleeding, and other local and systemic reactions) delivered by DCJI using an investigational spacer for ID delivery?
- 3. Will an investigational study arm of children receiving two reduced doses of 0.1 mL of vaccine administered IM by needle-syringe demonstrate *non-inferiority* to the immune responses achieved by the control arm of children receiving conventional, full-dose 0.25 mL administered by the same method in the same target tissue (obviating any need for intradermal delivery to achieve dose sparing)?

10. Investigational Plan

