10.1.3.2 Primary Safety

Primary safety endpoints are local and systemic reactions manifested for each of the following prompted adverse events during the intervals specified (see section 10.5.2.2).

Immediately after injection:

Local at injection site

- **Drop of blood** on skin
- Flow of blood on skin
- Wetness (not blood) on skin
- Other, may be entered and specified

\geq 30 -to- \leq 60 minutes after injection:

Local at injection site

- Erythema, largest diameter
- Swelling, largest diameter
- Induration, largest diameter
- Other, may be entered and specified
- Systemic
 - Fever, via axillary temperature
 - Sleepiness
 - Irritability
 - Seizures
 - Anaphylactic shock
 - Other, may be entered and specified

0-2 days and 3-7 days after injection:

Local at injection site

- Tenderness, 0 to 4 scale
- Redness, largest diameter
- Swelling, largest diameter
- Hematoma, largest diameter
- Midpoint circumference of limb (compared to baseline)

HIRRC/CDC Needle-free Intradermal	Page 38	File: 4785-ID-INF-Prot-Engl-2008Jun24.doc
Influenza Study - CDC-ISO-4785	of 138	2008-Jun-24

- Entire limb swelling
- Other, may be entered and specified

Systemic

- Fever, via axillary temperature
- Antipyretic medication given
- · Change in eating habits, loss of appetite
- Sleepiness
- Irritability
- Unusual or inconsolable crying
- Vomiting
- Diarrhea
- Seizures
- Other, may be entered and specified

8-28 days after injection:

Local at injection site or systemic

• Unprompted adverse events solicited on diary card and reported by any means

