10.4.6.3 Caching of Immediate Injection Site Observations by Nurses

To prevent unblinding of the physician investigators to the method of injection used, the immediate reactions observed by the unblinded injection nurses at the injection site (e.g., drop or flow of blood or wetness) for investigational doses 1 (Part 8, questions 1 to 8) and 2 (Part 11, questions 1 to 8) will be noted on separate colored pages (green 12enf and yellow 16enf, respectively) of the Case Report Form. For reasons of convenience, onto these removable colored pages will be moved other data items also completed by the nurses for dose 1 on page 11 (Part 7, questions 7 to 11) and for dose 2 on page 15 (Part 11, questions 7 to 11). For the injection, the nurses will separate and complete these pages and place them in a closed file in the injection room. After the investigational period of observation after dose 2, and after the physician investigator has entered all related assessments into the C.R.F. for a particular participant, these colored pages will be retrieved for insertion back into the rest of the C.R.F. and copied for forwarding to the CDC investigators for data entry and analysis.

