10.6.8 Vaccination Procedure

First, the injection nurses close the "injection cubicle" while the participant and parent remain outside. They open the **allocation group randomization envelope** (see section 10.4.4.3) for that child's dose (green for dose 1, yellow for dose 2, red for "insurance" dose 3). One injection nurse then shows the card to the other to confirm the dosage and method. Following the details described in section 10.4.2.3 above, the nurse duly prepares the syringe or jet injector cartridge, covers its tip to maintain cleanliness, and sets it down upon a clean surface and covers it.

The child is then brought into the "injection cubicle" and the parents are requested to remain outside. The **INF** vaccine is administered in the dose and route (ID or IM) specified by the randomization card into the anterolateral portion of the left thigh for children less than 12 months of age, or to the left deltoid muscle for children 12 months and older.

Immediately after the vaccination, the injection nurse will observe for several seconds the injection site for any wheal or bleb and any drops of blood or clear liquid, apply a band-aid, and duly note the information in the CRF, along with the time of injection. The *allocation card* is then destroyed and its pieces disposed into a paper shredder, and any remaining injection supplies or equipment removed from view.

The parent(s) and child are then reunited for holding and consoling (in the waiting area) during the subsequent minimum of 30 minutes of observation before reexamination of the injection site by the injection nurse (to avoid unblinding of the physican investigator from any temporary skin dimpling from the injector flange). During the post-vaccination waiting period, the parent/guardian will receive a final briefing and further training for aspects covered in section 10.6.4 above and reminded when to return next to the study center.

HIRRC/CDC Needle-free Intradermal	Page 94	File: 4785-ID-INF-Prot-Engl-2008Jun24.doc
Influenza Study - CDC-ISO-4785	of 138	2008-Jun-24

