At least 30 minutes following vaccination, the injection nurse will note any immediate or early local adverse events and complete the remaining data in parts 7, 11, or 15 of Case Report Form (CRF) ("Medical Exam and $[1^{st}/2^{nd}/3^{rd}]$ Vaccination") and questions 1 through 8 of Parts 8 and 12 of the CRF ("Local Immediate Reactions"). In the event of an unexpected immediate local reaction – such as frank bleeding or laceration – the physician will be notified to institute needed medical care, take a photograph, and make appropriate entries in the adverse event section of the CRF. In all cases, the physician investigator will assess questions 10 through 15 of CRF parts 8 and 12 ("Immediate Systemic Reactions"). The parent and participant will then be discharged from the study center.

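### Section 10.4.6 says unblinded staff record no adverse events, but the unblinded injection nurse records the immediate and 30–60-minute local primary safety endpoints

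*Protocol*

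**What the plan says.** Section 10.4.6 names two unblinded roles, the injection nurse and the holding assistant, and says: "None of these unblinded staff will be involved in assessing or recording adverse events in the Case Report or other forms". It adds that the clinical staff who assess and record reactions do not know the child's group.

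Two other places describe the work of the injection nurse.

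- Section 10.4.6.3 refers to "the immediate reactions observed by the unblinded injection nurses at the injection site", giving blood and wetness as examples. The nurses enter these on coloured CRF pages, which are held back from the physician and later sent to the sponsor for analysis.
- Section 10.6.8 has the injection nurse look, straight after the injection, for "any drops of blood or clear liquid, apply a band-aid, and duly note the information in the CRF". After at least 30 minutes it provides for "reexamination of the injection site by the injection nurse (to avoid unblinding of the physican investigator from any temporary skin dimpling", and at that point "the injection nurse will note any immediate or early local adverse events".

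Section 10.1.3.2 gives these observations their status: "Primary safety endpoints are local and systemic reactions manifested for each of the following prompted adverse events during the intervals specified". Its immediate list holds drop of blood, flow of blood and wetness. Its 30–60-minute local list holds erythema, swelling and "Induration, largest diameter".

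Research question 2 in section 9.6.4 asks about the "safety profile of jet-injected, reduced-dose, intradermal influenza vaccination (erythema, induration, limb swelling, bleeding, and other local and systemic reactions".

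**The concern.** The trial compares a jet injector with needle and syringe, and research question 2 asks about the local safety of the jet injector. A reader who relies on 10.4.6 will take every primary safety endpoint to have been assessed by someone unaware of the device. For the earliest local endpoints the assessor opened the allocation envelope and gave the injection.

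The protocol itself treats such knowledge as a threat. Section 10.4.6.2 justifies separating parent from child on the ground that parents who know the method may report with unconscious bias. The same reasoning applies to a nurse measuring a diameter. Presence of blood or wetness is fairly objective; the diameters of erythema, swelling and induration leave more room for judgement.

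**Working it through.** No rate, margin or sample size enters this point. The check is a comparison of the sections.

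**Step 1: does the injection nurse know the allocation?** Yes. Section 10.4.6 lists her as unblinded, and section 10.4.4.4 has her open the randomization envelope.

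**Step 2: who assesses each early endpoint?**

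| Window (10.1.3.2) | Items | Assessor | Source |
|---|---|---|---|
| Immediate, local | drop of blood, flow of blood, wetness | unblinded injection nurse | 10.4.6.3, 10.6.8 |
| 30–60 minutes, local | erythema, swelling, induration | unblinded injection nurse | 10.6.8 |
| 30–60 minutes, systemic | fever, sleepiness, irritability, seizures, anaphylactic shock | physician investigator for the immediate systemic questions | 10.6.8 |

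The first two rows contradict 10.4.6 and the third does not. Since 10.1.3.2 itself classes the items as prompted adverse events, they cannot be excused as something else.

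**Step 3: is an exception stated?** Section 10.4.6.3 discloses the nurse's role for the immediate reactions, but does not say that it qualifies the general sentence, and it does not mention the 30–60-minute re-examination. That appears only in 10.6.8. The two sections also differ on the CRF part for the dose 2 immediate local questions: Part 11 in 10.4.6.3, Part 12 in 10.6.8. The synopsis (Measurements of safety) describes the findings at 0 and 30–60 minutes as observed by the investigator, although 10.4.6 blinds the investigators.

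**Step 4: are later assessments separated from the unblinded nurses?** No section assigns later visits or diaries to the injection nurse. However, section 10.5.2.1 has nurses help parents complete the diary cards at visits, by telephone or at home. Section 10.6.3 says that the clinic nurses who act as study nurses are the ones trained to vaccinate unblinded. No section says that the nurse helping with a diary must be different from the one who injected the child. Only the sentence in 10.4.6 implies it, and steps 2 and 3 show that sentence to be inaccurate elsewhere.

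**Step 5: induration.** Section 10.1.3.2 lists induration at 30–60 minutes only; its lists for days 0–2 and 3–7 omit it. Yet the synopsis and section 10.5.2.1 have parents record induration in the diary, which runs for 8 days in the synopsis. Section 10.10 uses induration above 5 cm as one criterion for an arm's progression to phase II. As listed, the only primary-endpoint window for induration is the one assessed by the unblinded nurse, although later data are collected.

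**The case against.** The best defence is that the arrangement is intended and partly disclosed. Section 10.4.6.3 lies within the Blinding section and openly calls the nurses unblinded. Section 10.6.8 gives the reason for the nurse's re-examination: marks from the injector flange could reveal the device to the physician. This stands, and the procedure itself is not criticised. It does not make the nurse's assessment blinded, and 10.4.6 still says something untrue for these endpoints.

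It can also be said that blood and wetness are seen within seconds of injection, so no later blinded assessment could exist. That is right. The absence of a later time point for those three items is no gap, and only their label is at issue.

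The wording of the synopsis may mean no more than observation by study staff, in contrast to the parent diary. That reading is possible, so the synopsis is only supporting evidence.

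Three stronger readings are tempting, and the documents do not support them.

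- A reader might infer that later visits and diaries are also assessed unblinded. Nothing assigns them to the injection nurse; the text only fails to separate the roles clearly. Nor does it support the opposite claim that they are certainly unaffected.
- A reader might infer that the phase II induration criterion rests on unblinded data. Section 10.10 is not restricted to the 30–60-minute window, and the diary collects induration afterwards.
- A reader might infer that the early comparison is biased by some amount or in some direction. The protocol gives nothing from which to estimate either.

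**Conclusion.** The contradiction is real. Section 10.4.6 claims a blinding property that the design does not have for six named local primary safety endpoints: three immediate and three at 30–60 minutes, after each of the two investigational doses. These should be described as assessed unblinded. The immediate systemic questions assigned to the physician and the blinded HI assay are outside the point. Later visits and diaries are a matter of unclear separation, not shown unblinding.

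The consequence is for what may be claimed about local safety, especially in answer to research question 2. It should be corrected but does not threaten the trial. The conclusion rests on reading the sections as they stand and assumes that no other document assigns the early local assessments to a blinded person.

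**What to change.** 1. **Section 10.4.6 and the synopsis.** State that the immediate and 30–60-minute local reactions are recorded by the unblinded injection nurse so that the physician stays blinded. Keep the bar for all other adverse event recording. State that a nurse who gave, or held the child for, any of that child's injections does not assist with that child's diary or later assessments. Bring the synopsis wording on who observes at 0 and 30–60 minutes into line, and reconcile the CRF part number for dose 2.
2. **Reporting.** Label the six early local endpoints as unblinded, and base the observer-blinded reactogenicity comparison on physician visits and parent diaries.
3. **Section 10.1.3.2.** Add induration to the lists for days 0–2 and 3–7, since it is already collected and section 10.10 uses it.

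The cost is wording and labelling, with no new data. The separation of nurses may need some rostering. The protocol version is dated 24 June 2008 and does not state enrolment status; if follow-up is complete, the text should instead record who in fact assisted with diaries.

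Separate editorial note: section 10.4.4.1 gives 3! × 3! = 36 possible orders for a block of six. With two places for each of three arms, the number is 6!/(2! × 2! × 2!) = 720/8 = 90. This has no bearing on the point above.

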10.4.6.1 Premature "Breaking" of the Allocation Code

The coding list maintained by the independent outside party and other member(s) of the DSMB (see section 10.4.4) will not be divulged to anyone outside the DSMB, except at the conclusion of the clinical and laboratory aspects of each phase of the study, or on an emergency basis upon request from the U.S. or Dominican Principal Investigators.

In case of emergency requiring immediate knowledge of the method of influenza vaccination for a particular study participant in order to provide appropriate treatment or care, and upon request by the Dominican Principal or Senior Investigator, the blue envelope corresponding to the child's study identification number shall be produced by the hospital director and opened. Such an occurrence shall be reported to the U.S. Principal Investigator.

10.4.6.2 Separation of Parent from Child during Injection

As the careful, credible assessment of adverse events are important for scientific credibility, which determines its usefulness for public health policymakers, it is necessary to ensure the parents are blinded to the treatment group of their child until after the study is completed. Observations and reports by the parents are a significant component of the study. If parents are aware of the vaccination method used, their reports my be subconsciously biased, and they may inadvertently unblind the investigators through a casual comment or question, further undermining objectivity of the study findings.

Unlike other vaccine trials where the investigational product and the control product or placebo are both administered in a syringe, in this study the method of administration itself is under investigation and not easily concealed. The psychological discomfort of both child and parent that may be caused by the brief 1-to-2 minute separation are deemed an unfortunate but necessary requirement for the study, for which the parents will be thoroughly informed in advance and their voluntary consent required to participate. Alternative blinding methods that might have permitted the parent to remain in the injection room with the child were considered, but deemed unsatisfactory:

• Multiple injections on each visit. This method has been used in prior studies by others, in which every patient gets injected on every visit with both methods of

HIRRC/CDC Needle-free Intradermal	Page 74	File: 4785-ID-INF-Prot-Engl-2008Jun24.doc
Influenza Study - CDC-ISO-4785	of 138	2008-Jun-24

injection, only one of which contains the drug of interest, and the other saline placebo. In our study, this would require administration of a needle-syringe IM (intramuscular) injection and a jet injector ID injection for every injection visit. An unblinded pharmacist or other health worker outside the parent's and investigator's view would fill only one of these with the influenza vaccine, according to the randomization group, and the other device with a placebo of similar appearance.

Although perfectly controlled and thus valid from a scientific perspective, this method of blinding was rejected as causing twice as much psychological and physical discomfort than otherwise needed to satisfactorily answer the research questions.

• Blindfolding and earmuffing the parent in the injection room. Blindfolding the parent, who could be visible to the child in the room, would not be sufficient as a blinding method, as the jet injector makes a "poof" of noise. Masking that sound with electrically-powered, noise-cancelling headphones playing masking music into the parent's ears was considered. Alternatively, a simultaneous jet injector could be fired into the air by a third unblinded health worker, so that all parents heard the noise, regardless of study group allocation.

Blindfolding (with or without earmuffing) was rejected as demeaning to the parent and potentially frightening to the child. Simultaneous firing of a jet injector for those receiving needle injections was rejected as (1) labor-intensive, (2) potentially ineffective for blinding if needle injection (and patient recoil) and jet firing are not exactly simultaneous, (3) time-consuming, and (4) prone to medical error, such as inadvertent confusion of a jet cartridge filled with tap water for a mock injection into the air with a cartridge to be used to administer actual vaccine to a child in the ID-JI-0.1 group.

Standard practice in the Dominican Republic is for parents to be absent during certain pediatric procedures, particularly delicate or painful ones, such as phlebotomy and tympanocentesis, for which informed-consent otitis media studies are now being performed with parents absent from the treatment room.

Beyond the need for blinding, other reasons to avoid the parent holding the child during the injection have been provided by the U.S. Naval Medical Research Center (NMRC) pediatrician, IRB member, and principal investigator of a prior study of the Biojector with investigational ID spacer, [name].^{Epstein2002} Since the sound of the injector might cause the parent to release firm hold on the child, it was suggested that the child should be restrained instead by a trained nurse aware of the manufacturer's instructions that the limb and injection not move in relation to each other during the 1/3 second that the injection requires, to avoid any risk of laceration.

Other informed-consent trials with parents excluded from the vaccination room have been performed when the investigational vaccine could not otherwise be blinded. These included a recent trial of the intranasal FluMist[®] influenza vaccine squirted into the nose, compared to an injected vaccine.^{King2006} Other influenza vaccine studies have been done in children without parents present for the vaccination, and with such absence duly consented in advance.^{Khan1996, Rudenko1993, Tanaka1993}

The consent form advises the parents of the need to be separated from the child, just outside the door of the injection room, for the estimated 1 to 2 minutes to prepare and administer each of the first three study injections. The consent form permits them the opportunity freely to withdraw consent in advance of the study (and thus not to enroll), or to withdraw at any time during the study.

Phlebotomy. The presence or absence of the parents during the required three blood collections in this study would not affect blinding of the study. In keeping with common pediatric practice in the Dominican Republic and in most U.S. medical facilities, the parents will be requested, for their own peace of mind, to remain outside the room where phlebotomy and similar uncomfortable or frightening diagnostic (e.g., lumbar puncture) or therapeutic (e.g., tympanocentesis, surgery) treatments are performed. However, in this study, if the parents request to be present during phlebotomy, they will be permitted to do so, and this option is mentioned in the consent form.

